**Study Day 266 (PILOT) + 196 (MAIN) ( $\pm 7$  days; 140 days after Vaccination #3)**

1. Perform basic history and focused physical examination, emphasizing examination of any acute complaints.
2. Record vital signs (blood pressure, temperature, and heart rate).
3. Record AEs and concomitant medications, if applicable.
4. Obtain approximately 1.5 mL of blood for malaria blood smear and malaria PCR.

**Study Day 280 (PILOT) + 210 (MAIN) ( $\pm 7$  days; 154 days after Vaccination #3)**

1. Perform basic history and focused physical examination, emphasizing examination of any acute complaints.
2. Record vital signs (blood pressure, temperature, and heart rate).
3. Record AEs and concomitant medications, if applicable.
4. Obtain approximately 1.5 mL of blood for malaria blood smear and malaria PCR.

**Study Day 294 (PILOT) + 224 (MAIN) ( $\pm 28$  days; 168 days after Vaccination #3)**

1. Perform basic history and focused physical examination, emphasizing examination of any acute complaints.
2. Record vital signs (blood pressure, temperature, and heart rate).
3. Record AEs and concomitant medications, if applicable.
4. Obtain approximately 7.5 mL of blood for malaria blood smear, malaria PCR, anti-Pfs230 antibody ELISA, standard membrane feeding assay (SMFA), and transcriptional analysis.

**Study Day 378 (PILOT) + 308(MAIN) ( $\pm$ 56 days; 252 days after Vaccination #3)**

1. Perform basic history and focused physical examination, emphasizing examination of any acute complaints.
2. Record vital signs (blood pressure, temperature, and heart rate).
3. Record AEs and concomitant medications, if applicable.
4. Obtain approximately 6.5 mL of blood for malaria blood smear, malaria PCR, anti-Pfs230 antibody ELISA, standard membrane feeding assay (SMFA).

**Study Day 462 (PILOT) + 392 (MAIN) ( $\pm$ 56 days; 336 days after Vaccination #3)**

1. Perform basic history and focused physical examination, emphasizing examination of any acute complaints.
2. Record vital signs (blood pressure, temperature, and heart rate).
3. Record AEs and concomitant medications, if applicable.
4. Obtain approximately 6.5 mL of blood for malaria blood smear, malaria PCR, anti-Pfs230 antibody ELISA, standard membrane feeding assay (SMFA).

**Study Day 434 (PILOT 308 days post Vaccination #3) + 378 (MAIN 322 days after Vaccination #3) ( $\pm$ 84 days)**

1. Reconsent for continuation on study.
2. Perform basic history and focused physical examination, emphasizing examination of any acute complaints.
3. Record vital signs (blood pressure, temperature, and heart rate).
4. Record AEs and concomitant medications, if applicable.
5. Obtain approximately 14 mL of blood for CBC with differential and platelet count, ALT, creatinine, HIV, malaria blood smear, malaria PCR, anti-Pfs230 antibody ELISA, standard membrane feeding assay (SMFA) and transcriptional analysis.
6. For females, obtain a urine or serum sample for  $\beta$ -hCG testing. Ensure that the test is negative before proceeding.

**Study Day 448 (PILOT) + 392 (MAIN) ( $\pm$ 112 days; day of Vaccination #4)**

The following evaluations/procedures will be completed before vaccination:

1. Perform interim history and physical examination, focusing on any acute complaints.
2. Record vital signs (blood pressure, temperature, and heart rate).
3. During the physical examination, study staff will educate the subject regarding signs and symptoms of potential adverse events (AEs) and indications for use of antipyretics if fever, headache, or malaise occurs.
4. For females, obtain a urine or serum sample for  $\beta$ -hCG testing. Ensure that the test is negative before vaccinating.
5. For females, ensure agreement and compliance with pregnancy prevention before vaccinating.
6. Obtain approximately 11 mL of blood for CBC with differential and platelet count, ALT, creatinine, malaria blood smear, malaria PCR, anti-Pfs230 antibody ELISA, and standard membrane feeding assay (SMFA).
7. Confirm continued eligibility to receive vaccination.
8. Administer the vaccine.

The following evaluations/procedures will be completed following vaccination:

1. Observe the subject for at least 30 minutes after vaccination to evaluate immediate adverse reactions.
2. Record vital signs (blood pressure, temperature, and heart rate).
3. Perform interim history and physical examination, focusing on any acute complaints.
4. Record AEs and concomitant medications, if applicable.

**Study Day 451 (PILOT) + 395 (MAIN) ( $\pm 1$  day; 3 days after Vaccination #4)**

1. Perform basic history and focused physical examination (including injection site), emphasizing examination of any acute complaints.
2. Record vital signs (blood pressure, temperature, and heart rate).
3. Record AEs and concomitant medications, if applicable.
4. Obtain approximately 6.0 mL of blood for CBC with differential and platelet count, ALT, creatinine, and transcriptional analysis.

**Study Day 455 (PILOT) + 399 (MAIN) ( $\pm 2$  day; 7 days after Vaccination #4)**

1. Perform basic history and focused physical examination (including injection site), emphasizing examination of any acute complaints.
2. Record vital signs (blood pressure, temperature, and heart rate).
3. Record AEs and concomitant medications, if applicable.
4. Obtain approximately 5.0 mL of blood for standard membrane feeding assay (SMFA).

**Study Day 462 (PILOT) + 406 (MAIN) ( $\pm 7$  days; 14 days after Vaccination #4)**

1. Perform basic history and focused physical examination, emphasizing examination of any acute complaints.
2. Record vital signs (blood pressure, temperature, and heart rate).
3. Record AEs and concomitant medications, if applicable.
4. For females, obtain a urine or serum sample for  $\beta$ -hCG testing. Ensure that the test is negative before proceeding.
5. Obtain approximately 17 mL of blood for CBC with differential and platelet count, ALT, creatinine, malaria blood smear, malaria PCR, anti-Pfs230 antibody ELISA, standard membrane feeding assay (SMFA) and Transcriptional analysis.
6. Feeding evaluations (DSF) will also be performed at this visit.
  - a. Confirm eligible for DSF

**Study Day 476 (PILOT) + 420 (MAIN) ( $\pm 7$  days; 28 days after Vaccination #4)**

1. Perform basic history and focused physical examination, emphasizing examination of any acute complaints.
2. Record vital signs (blood pressure, temperature, and heart rate).
3. Record AEs and concomitant medications, if applicable.
4. Obtain approximately 1 mL of blood for malaria blood smear, and malaria PCR.
5. Feeding evaluations (DSF) will also be performed at this visit.
  - a. Confirm eligible for DSF

**Study Day 490 (PILOT) + 434 (MAIN) ( $\pm 7$  days; 42 days after Vaccination #4)**

1. Perform basic history and focused physical examination, emphasizing examination of any acute complaints.
2. Record vital signs (blood pressure, temperature, and heart rate).
3. Record AEs and concomitant medications, if applicable.
4. For females, obtain a urine or serum sample for  $\beta$ -hCG testing. Ensure that the test is negative before proceeding.
5. Obtain approximately 1 mL of blood for malaria blood smear, and malaria PCR.
6. Feeding evaluations (DSF) will also be performed at this visit.
  - a. Confirm eligible for DSF

**Study Day 504 (PILOT) + 448 (MAIN) ( $\pm 7$  days; 56 days after Vaccination #4)**

1. Perform basic history and focused physical examination, emphasizing examination of any acute complaints.
2. Record vital signs (blood pressure, temperature, and heart rate).
3. Record AEs and concomitant medications, if applicable.
4. Obtain approximately 6 mL of blood for malaria blood smear, malaria PCR, anti-Pfs230 antibody ELISA, standard membrane feeding assay (SMFA).
5. Feeding evaluations (DSF) will also be performed at this visit.
  - a. Confirm eligible for DSF

**Study Day 518 (PILOT) + 462 (MAIN) ( $\pm 7$  days; 70 days after Vaccination #4)**

1. Perform basic history and focused physical examination, emphasizing examination of any acute complaints.
2. Record vital signs (blood pressure, temperature, and heart rate).
3. Record AEs and concomitant medications, if applicable.
4. For females, obtain a urine or serum sample for  $\beta$ -hCG testing. Ensure that the test is negative before proceeding.
5. Obtain approximately 1 mL of blood for malaria blood smear, and malaria PCR.
6. Feeding evaluations (DSF) will also be performed at this visit.
  - b. Confirm eligible for DSF

**Study Day 532 (PILOT) + 476 (MAIN) ( $\pm 7$  days; 84 days after Vaccination #4)**

1. Perform basic history and focused physical examination, emphasizing examination of any acute complaints.
2. Record vital signs (blood pressure, temperature, and heart rate).
3. Record AEs and concomitant medications, if applicable.
4. Obtain approximately 1 mL of blood for malaria blood smear, malaria PCR.
5. Feeding evaluations (DSF) will also be performed at this visit.
  - a. Confirm eligible for DSF

**Study Day 546 (PILOT) + 490 (MAIN) ( $\pm 7$  days; 98 days after Vaccination #4)**

1. Perform basic history and focused physical examination, emphasizing examination of any acute complaints.
2. Record vital signs (blood pressure, temperature, and heart rate).
3. Record AEs and concomitant medications, if applicable.

4. For females, obtain a urine or serum sample for  $\beta$ -hCG testing. Ensure that the test is negative before proceeding.
5. Obtain approximately 1 mL of blood for malaria blood smear and malaria PCR.
6. Feeding evaluations (DSF) will also be performed at this visit.
  - a. Confirm eligible for DSF

**Study Day 560 (PILOT) + 504 (MAIN) ( $\pm 7$  days; 112 days after Vaccination #4)**

1. Perform basic history and focused physical examination, emphasizing examination of any acute complaints.
2. Record vital signs (blood pressure, temperature, and heart rate).
3. Record AEs and concomitant medications, if applicable.
4. Obtain approximately 6 mL of blood for malaria blood smear, malaria PCR, anti-Pfs230 antibody ELISA, standard membrane feeding assay (SMFA).
5. Feeding evaluations (DSF) will also be performed at this visit.
  - a. Confirm eligible for DSF

**Study Day 574 (PILOT) + 518(MAIN) ( $\pm 7$  days; 126 days after Vaccination #4)**

1. Perform basic history and focused physical examination, emphasizing examination of any acute complaints.
2. Record vital signs (blood pressure, temperature, and heart rate).
3. Record AEs and concomitant medications, if applicable.
4. For females, obtain a urine or serum sample for  $\beta$ -hCG testing. Ensure that the test is negative before proceeding.
5. Obtain approximately 1 mL of blood for malaria blood smear and malaria PCR.
6. Feeding evaluations (DSF) will also be performed at this visit.
  - a. Confirm eligible for DSF

**Study Day 588 (PILOT) + 532 (MAIN) ( $\pm 7$  days; 140 days after Vaccination #4)**

1. Perform basic history and focused physical examination, emphasizing examination of any acute complaints.
2. Record vital signs (blood pressure, temperature, and heart rate).
3. Record AEs and concomitant medications, if applicable.
4. Obtain approximately 1 mL of blood for malaria blood smear and malaria PCR.
5. Feeding evaluations (DSF) will also be performed at this visit.
  - a. Confirm eligible for DSF

**Study Day 602 (PILOT) + 546 (MAIN) ( $\pm 28$  days; 154 days after Vaccination #4)**

1. Perform basic history and focused physical examination, emphasizing examination of any acute complaints.
2. Record vital signs (blood pressure, temperature, and heart rate).
3. Record AEs and concomitant medications, if applicable.
4. Obtain approximately 1 mL of blood for malaria blood smear and malaria PCR.
5. Scheduled unblinding of VU
  - a. If received Pfs230D1M-EPA/ASO1 offer meningitis comparator vaccination

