### 3.3.2 Immunogenicity in Healthy Malian Children

Anti-Pfs230 antibody testing was implemented to be conducted in Mali in early 2020. At the time of the fourth dose amendment (V5.0) ELISA assays from the Pilot Phase (Pediatric Arms, n=30 9-18 years old, n=30 5-8 years old; 1:1 randomization to Pfs230D1M-EPA/AS0, n=15/age arm and comparator, n=15/age arm) have been completed prior to premature cessation of laboratory activities secondary to COVID-19 pandemic. [Figure 21](#) presents the antibody responses seen in the evaluated population (both 9-18 yo Pilot Phase subjects and 5-8 yo Pilot Phase subjects). Children, on initial analysis, appear to have similar antibody responses to Pfs230D1M-EPA/AS01 vaccine as healthy adults.

**Figure 21. Comparison of Pfs230D1M-EPA/AS01, 40 ug, in Healthy Malian Adults (17-I-N006) to Healthy Malian Children [5-8 year olds (green), 9-18 year olds (purple)] (19-I-N086).**

For 19-I-N086, only blinded data are presented given study status; figure represents only those values above the level of ELISA detection.

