Vaccination #3 = study day 112/42 for Arms 2a/2b, 3a/3b; for Arms 4a/4b this is study day -14). Preteen and adolescent subjects in Arms 1a/1b, 3c/3d will also be assessed by DSF for vaccine activity starting 2 weeks post receipt of vaccination #3; DSFs will be completed every 2 weeks for a total of 8 DSFs.

All enrolled subjects (Groups 1-4, except adults on a less regular active follow-up) from the family compound will be monitored for patent parasitemia every 2 weeks, and during unscheduled visits if clinically indicated, for at least 6 months up to 12 months post vaccination, with time to patent parasitemia being evaluated as a vaccine efficacy timepoint in children 1-8 years of age as well as 9-18 years of age within the compounds (separate secondary evaluation given expected nighttime mobility and no pre-transmission season AL treatment).

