## 8.3 Sample Size and Estimated Duration of Study

A total of 60 subjects will be vaccinated in the age de-escalation pilot phase of the trial. At the time of enrollment, all children will receive a treatment course of AL prior to first vaccination and will be randomized at the time of vaccination #1. Since children may be replaced if enrolled but not randomized, more subjects may be initially enrolled, but no more than 60 subjects will

receive at least 1 vaccine. Each subject will be monitored actively for at least 12 months after the last vaccination, for a total of 13 to 18 months of participation depending on timing of screening for the study. Up to 80 subjects will be screened to accommodate possible screening failures.

For the main phase of the study, approximately 137 total compounds/vaccine units will be approached for enrollment for an estimated total of ~1500 vaccinated subjects 5 years of age and older and ~400 subjects 1-4 years of age. Given each compound is of a variable population (ranging from 5-90+ years of age), this is an estimate of enrollment with expected enrollment in the total main phase to be ~1500 subjects +/- 15%. Subjects will be monitored actively for at least 12 months after the last vaccination, for a total of 13 to 18 months of study participation depending on timing of screening for the study. Up to 2380 subjects will be screened to accommodate possible screening failures.

For the fourth dose and continuation on study, the enrolled compounds/vaccine units will be approached for re-consenting and re-screening. No new enrollments will be permitted. Despite adjusted ages over the last year, subjects will remain in their assigned arms from enrollment for evaluation of study endpoints (e.g. DSFs, blood smears), receipt of AL, and receipt of vaccinations. All subjects who received at least 1 vaccination during 2019-2020 and are on study may be eligible for continuation. All enrolled children (1-4 year olds) who received antimalarial treatment with their VU will be eligible for continuation. Subjects not wanting to continue on study for another year or are found to be ineligible will not be unblinded until the end of Year 2, and will be provided the opportunity to complete a final visit with their VU at that time.

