#### 8.4 Study Definitions

**Screened:** Subjects will receive a screening identification number (SC-XXX-XXX) when the informed consent is signed, and will either be determined as “enrolled” or “screen failures” as noted below; subjects within the same vaccine unit will be noted by the same first 3 numbers (SC-XXX-xxx) of their screening identification.

- Screening may be completed over the course of multiple visits.
- Screening will occur within 56 days prior to enrollment into the study.
- If the screening visit is >56 days prior to enrollment (determined by the date of each component), then an updated medical review, physical exam/vital signs, repeat Malaria Comprehension Exam, and repeat laboratory evaluation (inclusive of safety labs, human immunodeficiency virus [HIV], EKG) will be completed to determine eligibility for enrollment.

**Enrolled:** Subjects will be considered enrolled beginning with the receipt of the first blood draw and first AL dose.

- Final study number assigned – MV-19-XXX-XXX-X [MV-19-(vaccine unit #)-(study # per age)-(letter for QC)]
  - Given the last three numbers of the study number are dependent on age and requirement by the electronic database to have a study number during screening, if a child/young adult changes age categorization (4→5-year-old, 8→9-year-old, 18→19-year old) between screening and enrollment a new study ID will be assigned categorizing the study subject as above. The screening identification number will not change.

**Randomized:** Subjects are considered randomized when their family compound/vaccine unit undergoes randomization collectively at the time of first vaccination of their first family member. A compound/family may be randomized once the following criteria are met:

- Approximately 80% of the family compound/vaccine unit preliminarily eligible to be vaccinated has signed consent, agreed to participate in the study, and has been found preliminarily eligible for enrollment
- Entire family/compound will be randomized as a collective whole at the time of first vaccination in any family compound/vaccine unit participant
- To note: prior to the start of the study, the study geographers, based off GPS coordinates and village census assigned family compounds into vaccine units which were randomized as a unit.

**Re-enrolled:** Subjects are considered re-enrolled for Year 2 of follow-up when they complete the following:

- Re-consent

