1 Visit windows are based off timing of days post the preceding vaccination; broad visit window in place for Booster dose in attempt to group VU together and provide flexibility given the ongoing COVID pandemic 2 SMFA may be completed on subjects at Study Day 336 and 448; other SMFA time points indicated above will be completed depending on associated ELISA and DSF results at that time point. 3 DSF will be completed twice monthly post Vaccination #4 from day 406 through 532 (total = 10 feeds).																					

Year 2: Arms 3e/3f (≥19 years of age)

Arms 3e/3f (Adults 19 years of age and older)		Months	13.5	14				15	16	18	20	23	26
		Visits	24	25	26	27	28	29	30	31	32	33	34
Procedures	Blood Volume	Study Day	378 (Rescreening)	392	395	399	406	420	448	504	560	644	728
		Days post Vac	322	336/0	3	7	14	28	56	112	168	252	336
		Visit Windows (days) (1)	±84	±112	±1	±2	±7	±7	±7	±7	±28	±56	±56
Clinical Procedures													
Updated medical history/ physical													
Reconsent			X										
Pre-test/Post-test HIV counseling			X										
Interim clinical evaluation			X	X	X	X	X	X	X	X	X	X	X
AE/SAE assessment			X	X	X	X	X	X	X	X	X	X	X
Pregnancy Prevention			X	X	X	X	X	X	X	X	X	X	X
Conmed review			X	X	X	X	X	X	X	X	X	X	X
VACCINATION			X										
Unblinding											X		
Laboratory Procedures													
CBC with differential	EDTA		2	2	2		2						
ALT/ Creatinine	SST			3	3		3						
HIV testing	SST		5										
Urine/Serum pregnancy test (females only)	Urine Container or SST		0.5	X									
Malaria Blood Smear	CAP/EDTA		0.5	0.5			0.5		0.5	0.5	0.5	0.5	0.5
Malaria PCR/Genotyping/ Gametocyte	CAP/EDTA		0.5	0.5			0.5		0.5	0.5	0.5	0.5	0.5
Pfs230 ELISA	SST		5	5		5	10		5	5	5	5	5
SMFA (2)													
Transcriptional analysis	PAXGene		1		1		1				1		
Daily blood draw volume in mL			12.5	11.0	6.0	5.0	17.0	0.0	6.0	6.0	7.0	6.0	6.0
Cumulative blood volume in mL			161.0	172.0	178.0	183.0	200.0	200.0	206.0	212.0	219.0	225.0	231.0
1 Visit windows are based off timing of days post the preceding vaccination; broad visit window in place for Booster dose in attempt to group VU together and provide flexibility given the ongoing COVID pandemic													
2 SMFA may be completed on subjects at Study Day 392 and 448; other SMFA time points indicated above will be completed depending on associated ELISA results at that time point.													

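### A vaccine unit can be unblinded before its last two-weekly smear and, at the edge of the visit windows, before its last direct skin feed

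*Combined protocol and SAP*

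**What the plan says.** Appendix B places "Scheduled unblinding of VU" at Day 546 ±28 for main-phase participants and Day 602 ±28 for the pilot. It does so for ages 9-18, ages 5-8, adults and (Day 546 only) ages 1-4. In the vaccinated arms this is 154 days after dose 4.

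For the 9-18-year-olds who supply the primary endpoint, the Appendix A footnote for Arms 3c/3d reads "DSF will be completed twice monthly post Vaccination #4 from day 406 through 532 (total = 10 feeds". Appendix B gives the tenth feed, at Day 532 (pilot 588), a ±7-day window. Section 17.3.2.1 intends to combine Years 1 and 2 for DSF.

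Blood-smear parasitemia is a secondary endpoint (Section 8.2.2). Section 7.2.2 plans two-weekly monitoring "for at least 6 months up to 12 months post vaccination". Smears are scheduled at 154, 168, 252 and 336 days after dose 4.

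Section 8.3 says that participants who do not continue, or who are ineligible, "will not be unblinded until the end of Year 2". Section 7.1 describes the trial as double-blind. Nothing in the text makes unblinding depend on a VU having finished its feeds or smears.

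**The concern.** Allocation is by VU, so telling one member the arm tells all of them. If that can happen while feeds or efficacy smears are still due, the final part of follow-up is no longer masked for that VU.

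The routes by which this could matter are behavioural:

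- A child may decline any feed and stay in the study (Section 12.6.4.), and the primary model offsets for the number of feeds performed (Sections 17.2.1 and 17.3.2.3). Attendance that differs by known arm therefore changes what is observed.
- Malaria is also detected at unscheduled sick visits and treated. Section 1.2.3 says artemether/lumefantrine can lower DSF positivity for at least four weeks, so altered care-seeking could affect feeds as well as smears.
- At unblinding only the Pfs230 arm is offered a meningitis vaccine, which adds an asymmetry during the remaining adverse-event follow-up.

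**Working it through.** **Inputs** (Appendices A and B, Year 2)

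| | Main | Pilot |
|---|---|---|
| Dose 4 | 392 | 448 |
| Last DSF and window (App. B) | 532 ±7 = 525 to 539 | 588 ±7 = 581 to 595 |
| VU unblinding and window (App. B) | 546 ±28 = 518 to 574 | 602 ±28 = 574 to 630 |
| Last two-weekly smear | 560 | 616 |

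**1. The plan's own figure.** Feeds every 14 days from Day 406 to Day 532: (532 − 406)/14 + 1 = 10. This reproduces the stated 10.

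**2. Nominal days.** Unblinding minus last feed: 546 − 532 = 14 days (pilot 602 − 588 = 14). No feed follows unblinding.

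**3. Window edges, Appendix B.** Last permitted feed day minus first permitted unblinding day: 539 − 518 = 21 days (pilot 595 − 574 = 21). Feeds with a nominal day on or after the opening are those on Days 518 and 532 (pilot 574 and 588), so at most 2 of 10 in Year 2. Over both years (8 + 10 = 18 feeds) this is 2/18 = 11%.

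**4. Window in Appendix A.** For Arms 3c/3d, Appendix A gives Day 546 ±7. Unblinding then opens on 546 − 7 = 539, and 539 − 539 = 0 days of overlap. On this reading one child's own visit no longer exposes a feed.

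**5. Staggered dosing within a VU.** Footnote 1 of the Year 2 tables counts windows from the preceding vaccination, and dose 4 has a ±112-day window. If another member was dosed *g* days before the child, that member's nominal unblinding visit falls 154 − *g* days after the child's dose. It precedes the tenth feed (140 days) when *g* > 14 and the ninth (126 days) when *g* > 28. Narrowing the Day 546 window does not remove this.

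**6. Smears.** The last two-weekly smear falls 560 − 546 = 14 days after nominal unblinding (pilot 616 − 602 = 14). In the 28-day months of Appendix A, unblinding is at 154/28 = 5.5 months and this smear at 168/28 = 6.0 months, so the smear lies within the six-month minimum. Even the ±7 window closes at Day 553, before nominal Day 560. Smears at 252 and 336 days after dose 4 (Days 644 and 728) also follow.

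**7. Day of unblinding in Appendix A.** Appendix A has no adult Day 546 visit; its columns run 504, 560, 644. So far as the table layout can be read, the unblinding mark is under Day 560 for adults (±28) and for ages 1-4 (±14). The adult window would then open on 560 − 28 = 532, still 7 days before Day 539. The ages 1-4 window would open on 560 − 14 = 546, after it.

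**The case against.** The strongest reply is that this is mainly a mismatch between appendices. Appendix B's adult Day 546 visit carries the 7.0 mL draw, transcriptional sample and ±28 window that Appendix A lists at Day 560. That suggests Day 560 may have been intended, in which case nominal unblinding coincides with the last two-weekly smear. For a single child, the ±28 edge would require the 154-day visit to happen before the 140-day visit. The wide dose-4 window is explained as a means of grouping VUs together, and no actual within-VU dosing gap is documented. Feeds use laboratory mosquitoes dissected in Bamako, and smears are prepared in duplicate by trained microscopists, so reading bias is less likely than for a subjective outcome. Year 1 feeds were already complete while the study was blinded.

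Most of this stands and limits the size of the point. It does not remove it: the text contains two windows, apparently two days, and no completion condition, and it does not say whether those reading smears or dissections stay masked.

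Three stronger readings are tempting but unsupported:

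- A reader might infer that 20% of Year 2 feeds follow unblinding as scheduled. On nominal days none do; two of ten is the window-edge maximum for one child's own visits.
- A reader might see a contradiction with Section 8.3. That sentence covers only participants who do not continue, and the end of Year 2 is not dated.
- A reader might infer that mid-trial ELISA results, with VU numbers embedded in study numbers, could reveal a VU's arm. Section 3.3.2 says "only blinded data are presented given study status; figure represents only those values above the level of ELISA detection", and nothing shows that field staff saw individual results. Nor would one high titre identify a VU. At a cut-off exceeded by 5% of baseline samples, a control VU of about 8 vaccinees (1101/137, using the planned VU count) has a 1 − 0.95^8 = 34% chance of at least one, assuming independence.

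**Conclusion.** The point holds as a gap in the masking rule. For the primary endpoint the exposure is conditional: up to 2 of 10 Year 2 feeds, within a 21-day overlap, if Appendix B's ±28 window applies and is used at its edge, or a feed or more if VU members receive dose 4 over 14 days apart. For the secondary smear endpoint, one two-weekly smear follows unblinding on Appendix B's nominal days and under either stated Day 546 window; if Day 560 was intended, the two coincide. The smear analysis period is not defined, so the number of post-unblinding smears entering the analysis cannot be determined. No bias has been measured. The case for change rests on the low cost of protecting a primary endpoint that combines both years.

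**What to change.** State one rule, identically in Appendices A and B and consistently with Section 8.3: a VU is unblinded only when every member of that VU has completed the last DSF and the last two-weekly smear (through the Day 560 visit, pilot 616), and those dissection and smear results are recorded and locked. Give the unblinding visit one day and one window across age groups, and date the end of Year 2 in Section 8.3 accordingly. Correct the Appendix B heading for the final visit of ages 9-18, which shows Day 588/518 for 336 days after dose 4, where Appendix A has Day 784/728. Say in Section 17 that smears taken after unblinding (Days 644 and 728) lie outside the blinded efficacy analysis.

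The cost is a delay of a few weeks in unblinding for some VUs, with no new visits. The meningitis-vaccine offer is tied to unblinding, so the sponsor would need to reconcile its timing.
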